Treatment With Cannabis Oil Containing Canabidiol (CBD) Only or 20:1 CBD:THC vs. Placebo of Persons Diagnosed With ADHD After Failure of Conventional Treatment

Date: 16/08/21 Protocol number: 232-19-ASF

Version 4

Background

ADHD is the most frequent neuro-developmental disorder in childhood affecting around 8% of children and continues into adolescence and adulthood for some 70% of them. In some cases, ADHD appears in adulthood.

There are 3 subtypes for this disorder:

Mainly inattentive, mainly hyperactive-impulsive and combined type.

Indicated drug treatments for ADHD fall into 2 categories: stimulants (such as

methylphenidate and amphetamines) and non-stimulants (such as atomoxetine, guanfacine and clonidine) but some patients cannot tolerate their side effects (decreased appetite and weight, insomnia, irritability, headache, fatigue, etc) or serious side effects like psychosis onset and CV complications or find them non effective in some 50% of the cases.

In the last decade, medical cannabis products have been researched as possible treatment for neurological and mental diseases such as: PTD, ASD, epilepsy, FM and more.

Data on the effects of cannabidiol rich cannabis extract use for ADHD seems promising but is still limited.

The aim of this study is to investigate if oral cannabinoids given to adults with ADHD affect the symptoms of the disorder. At the same time, side effects and DDI will be assessed.

In this trial, 3 different types of cannabis oil will be compared to a placebo drug.

Participants will be randomized to any of the 4 arms.

Objectives

Primary

To assess the efficacy of the cannabis oil treatment containing different concentrations of CBD, THC, CBDV, CBG as per TOVA and Conners test results.

Secondary

To assess side effects of cannabis treatments and to compare them with those of conventional drugs prescribed for ADHD.

To assess the quality of life of participants with ADHD treated with the different cannabis oils.

Methods

Participants will undergo a prescreening interview (phone and mail) which includes: inclusion/exclusion criteria, medical history and concomitant medications, previous treatments for ADHD. After assuring the eligibility to the study, the will be invited to take part in the study.

Each participant will attend three visits in the clinic and will be contacted by phone twice.

Visit 1: randomization, day 1

Actions and procedures:

- Consent process, including signing ICF
- inclusion/exclusion criteria
- Review of medical history and concomitant medications
- TOVA test
- Vital signs and physical examination
- Urine and blood test
- Questionnaires filling (eat, sleep, behavior)
- Randomization
- Drug dispense and instructions for use

Follow up: day $14 (\pm 3 \text{ days})$

• Adverse events, change in concomitant medications, blinding questionnaire

Visit 2: end of treatment, day 26 (± 2 days)

Actions and procedures:

- Adverse events, change in concomitant medications
- TOVA test
- Vital signs and physical examination
- Urine and blood test
- Questionnaires filling (eat, sleep, behavior)

Visit 3: follow up, day 42 (±2 days)

- Adverse events, change in concomitant medications
- Questionnaires filling (eat, sleep, behavior)

• Return of study drug

Dose regimen

Days 1-2: 10 drops/day (total 0.3 ml/day)*

Days 3-7: 20 drops/day (total 0.6 ml/day)

Days 8-21: 40 drops/day (total 1.2 ml/day)

Days 22-28: 60 drops/day (total 1.8 ml/day)

After day 28, dose will be tapered: 40 drops at day 29, 20 drops at day 30, 10 drops at days 31-32. Day 32 will be the last day of treatment.

*The volume of one drop is approx.0.03 ml.

Main inclusion criteria:

- Participants aged at least 18 years old diagnosed with ADHD by DSM
- -Participants with a smaller than 0 TOVA score or with a greater than 0 score that as per investigator opinion suffer from ADHD
- -Participants who experienced treatment failure with more than one ADHD conventional drug
- Participants willing to attend all the visits in the trial.

Main exclusion criteria:

- Participants who were treated with benzodiazepines or antihistamines in the week that preceded the trial start.
- -Participants suffering from neurologic or psychiatric diseases
- -Participants suffering from malignant diseases
- -Participants suffering from syndromes or metabolic diseases
- -Participants with significant clinical diagnosis that can damage the trial unfolding. The investigator may include them after the end of the situation which prevented their previous inclusion.
- -Participants breastfeeding, pregnant or not willing to use contraceptives.
- -Participants that will not follow the protocol as per investigator opinion.
- -Participants who weight less than 45 kg or more than 120kg or with BMI greater than 30

- -Participants participating in another clinical trial which includes drug treatment
- -Participants receiving any treatment for ADHD
- -Participants using drugs
- -Participants using cannabis or products containing cannabinoids, including medical cannabis.

Sample size calculation

In order to detect differences at p=0.05 with 80 % power, 53 participants in each arm (total of 212 participants) will be needed. With an estimation of 15% drop-out, 244 participants will be recruited.

Statistical analysis plan

Paired T-tests to assess longitudinal changes in scores before and under treatment will be performed for each participant.

In addition, results from the 4 arms will be compared.

Trial products

If possible the trial drugs will be dispensed with a syringe instead of a dropper. Dosage will stay identical and will be measured by volume.

table 1. Max. daily dose in mg of each cannabinoid in the different trial products

arm	CBG	CBDV	THC	CBD
	(mg/day)	(mg/day)	(mg/day)	(mg/day)
Placebo	0	0	0	0
Arm1	0	27	9	171
Arm 2	171	0	4.5	0
Arm 3	171	27	9	171

In arm 3 that contains higher dosages, a person weighing 45 kg (minimum for participating) and receiving the max dosage of 60 drops will get 3.8 mg/kg/day CBD and 0.2 mg/kg/day THC.

In special cases (for ex. extreme BMI) investigator will consider changing the dosage program from the standard in the trial in order to adapt them better to the participant.

Participants will keep a diary (hard copy or electronic) and fill in actual treatment ingestion.

In any case, daily dose will not exceed 400 mg CBD and 20 mg THC.

Placebo will have same package, color and taste as trial product.

Treatment cessation

Treatment cessation because of early termination will be done as described in dose regimen or as per researcher decision.

Bibliography

Coghill, D.R et al. Long-Term Safety and Efficacy of Lisdexamfetamine Dimesylate in Children and Adolescents with ADHD: A Phase IV, 2-Year, Open-Label Study in Europe. CNS Drugs 31, 625–638 (2017). https://doi.org/10.1007/s40263-017-0443-y

Cooper RE et al. Cannabinoids in attention-deficit/hyperactivity disorder: A randomised-controlled trial. European Neuropsychopharmacology Volume 27, Issue 8, August 2017

Devinsky, O et al. 2014. Cannabidiol: pharmacology and potential therapeutic role in epilepsy and other neuropsychiatric disorders. Epilepsia 55, 791–802. http://dx.doi.org/10.1111/epi.12631

Stone NL et al. Protective Effects of Cannabidivarin and Cannabigerol on Cells of the Blood–Brain Barrier Under Ischemic Conditions. Cannabis and Cannabinoid ResearchVolume 6, Number 4, 2021 Mary Ann Liebert, Inc.DOI: 10.1089/can.2020.0159

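### The secondary objective compares side effects with conventional ADHD drugs, but no arm receives one and no planned analysis contains a value under one

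*Combined protocol and SAP*

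**What the plan says.** Under Objectives (Secondary), the plan intends "To assess side effects of cannabis treatments and to compare them with those of conventional drugs prescribed for ADHD". The Background defines the comparison actually made: "In this trial, 3 different types of cannabis oil will be compared to a placebo drug". Table 1 under Trial products confirms four arms, one placebo and three oils.

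The remaining relevant text is:

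- **Eligibility.** The main exclusion criteria rule out "Participants receiving any treatment for ADHD". The main inclusion criteria require earlier failure of more than one conventional ADHD drug.
- **History.** The prescreening interview in Methods covers "medical history and concomitant medications, previous treatments for ADHD".
- **Adverse events.** They first appear at the day 14 follow-up ("Adverse events, change in concomitant medications, blinding questionnaire"), then at Visit 2 (day 26) and Visit 3 (day 42). Visit 1 does not list them.
- **Questionnaires.** Visits 1, 2 and 3 each include "Questionnaires filling (eat, sleep, behavior)".
- **Analysis.** The Statistical analysis plan has two elements: paired t-tests of scores before against during treatment, and a comparison of the four arms. No outside or historical reference is named.

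**The concern.** The objective names a comparator that the design does not contain, and does not name placebo, the comparator it does contain. Participants have already failed conventional drugs, so readers will look for a statement on whether the oils are easier to tolerate. The objective invites that statement.

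It could rest on only two things. One is participants' recalled experience of drugs that had failed them. The other is an outside source that, with none named now, could be picked after the results are known. Neither supports a claim that the oils are better or worse tolerated.

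**Working it through.** The plan gives no figure for this comparison, so there is none to reproduce. The check asks whether any part of the plan supplies a side-effect value under a conventional drug.

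**1. Arms** (Background; table 1). Placebo, Arm 1, Arm 2, Arm 3. Arms receiving a conventional drug: 0 of 4.

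**2. Status at entry** (Main exclusion criteria). Current ADHD treatment excludes, so none of the 244 planned participants should be on a conventional drug at entry. This follows from eligibility; it is not an observed count.

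**3. Adverse-event collection** (visit schedule). Days 14, 26 and 42: three contacts, all after randomisation to an oil or placebo.

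**4. Planned analyses** (Statistical analysis plan). Analyses containing a conventional-drug value: 0 of 2.

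- *Paired tests.* The earlier value is the Visit 1 value, from people not then receiving ADHD treatment. The contrast is oil (or placebo) against that state. The tests are also on scores, and adverse events are not listed at Visit 1. The eating, sleep and behaviour questionnaires do touch on the harms the Background attributes to conventional drugs ("decreased appetite and weight, insomnia, irritability, headache, fatigue"), but at Visit 1 they too are completed by people not on such a drug.
- *Four-arm comparison.* This contrasts oils and placebo only.

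**5. Treatment history** (Methods; Main inclusion criteria). It is not stated to include side effects. It comes from people selected for failure, which is not defined: the Background mentions intolerance and also says some patients "find them non effective in some 50% of the cases". Selection on intolerance would raise the recalled side-effect rate; incomplete recall would lower it. Events on the oils are collected prospectively. The net direction of bias is therefore unknown, and its size cannot be estimated because the documents give no side-effect rate for any drug or oil.

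**6. Outside source** (Bibliography). The one conventional-drug study listed is, by its title, a two-year open-label study in children and adolescents. This trial treats adults, with the last dose on day 32 (Dose regimen). No analysis refers to that study.

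**7. Precision of the contrast the trial can make.** Take the proportion of participants with an adverse event, oil against placebo. The 95% Wald half-width is

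1.96 × √[p₁(1 − p₁)/n + p₂(1 − p₂)/n],

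which is largest at p₁ = p₂ = 0.5, where it equals 1.96 × √(0.5/n). No event rate need be assumed.

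- Sample size: 53 × 4 = 212; 212 × 1.15 = 243.8, given as 244; 244/4 = 61 per arm if allocation is equal.
- n = 53: 1.96 × √(0.5/53) = 0.190, or 19 points.
- n = 61: 1.96 × √(0.5/61) = 0.177, or 18 points.
- n = 53 with Bonferroni adjustment for three oil–placebo contrasts: 2.394 × √(0.5/53) = 0.233, or 23 points.

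**The case against.** The strongest reply is that the objective never promises a randomised or formally tested comparison. Setting the oils' adverse events beside the known profile of conventional drugs is an ordinary reading: the Background lists those side effects, and the Bibliography includes a long-term safety study of one such drug. On this view the only gap is an unnamed source. Previous treatments are also recorded, failure must be established for every participant, and a short protocol may not spell out that the reasons for failure are noted.

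Part of this stands. A descriptive comparison is possible in principle, and the plan's silence does not prove that side effects of earlier drugs go unrecorded. No washout for ADHD drugs and no look-back period for the questionnaires is given, so the Visit 1 value is best described as not currently treated, rather than free of any carry-over. The four-arm comparison may already be meant to cover adverse events against placebo.

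It does not rescue a comparative conclusion. A fuller history would still be recalled and selected on failure, and the one cited study differs in age group, duration and design. The arms and the exclusion remove the comparator, so added analysis text cannot create concurrent data on it. It is also fair to say that the half-widths in the working do not bear on the missing comparator; they only guard against overselling the replacement.

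**Conclusion.** The concern holds. The side effects of the oils can be described and compared with placebo, but the comparison with conventional drugs cannot support a conclusion as designed. By count, 0 of 4 arms and 0 of 2 planned analyses supply a value under a conventional drug. The bias of any substitute comparison is of unknown size and direction.

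The consequence is limited to one clause of a secondary objective; efficacy and the randomised adverse-event data are untouched. The finding rests on the current exclusion being applied as written and on no comparator source being specified outside this document. The precision figures assume equal allocation and single, unadjusted Wald intervals, except the 23-point figure, which is Bonferroni-adjusted for three contrasts.

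**What to change.** Reword the objective along these lines: *to describe the side effects of each cannabis oil and compare the incidence of adverse events with placebo, as randomised (risk difference with 95% confidence interval)*. Add a matching line to the Statistical analysis plan, and say there that the intervals are for estimation and whether they are adjusted for three contrasts.

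Then either delete the conventional-drug clause, or keep it as a descriptive discussion against a source named before results are available, with a statement that no comparative conclusion will be drawn.

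The cost is one sentence in the objectives and one line in the analysis plan, with no new data collection. The sponsor gives up a comparative tolerability claim that the design could not have supported.

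### The TOVA entry rule sets little effective threshold on a primary measure, and nothing in the plan accounts for participants who enter above 0

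*Combined protocol and SAP*

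**What the plan says.** All references are to the combined protocol and SAP.

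- **Main inclusion criteria.** The TOVA rule is "Participants with a smaller than 0 TOVA score or with a greater than 0 score that as per investigator opinion suffer from ADHD". A separate criterion, applying to everyone, is "Participants aged at least 18 years old diagnosed with ADHD by DSM".
- **Objectives, Primary.** Efficacy is to be assessed "as per TOVA and Conners test results", so TOVA is both an entry variable and a primary measure.
- **Methods.** TOVA is listed before randomisation at Visit 1 and is repeated at Visit 2.
- **Background.** On allocation the text says "Participants will be randomized to any of the 4 arms". No stratification factor is named there or elsewhere.
- **Sample size calculation.** "In order to detect differences at p=0.05 with 80 % power, 53 participants in each arm (total of 212 participants) will be needed". No effect size, SD, test or target population is given.
- **Statistical analysis plan.** It has two sentences. The first is "Paired T-tests to assess longitudinal changes in scores before and under treatment will be performed for each participant". The second says that the four arms will be compared, without a method. Neither mentions baseline TOVA as a covariate, subgroup or interaction.

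The documents do not define the TOVA score, say what 0 represents, or label any range as impaired or unimpaired.

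**The concern.** The rule is written as a TOVA criterion, but the score decides very little. Below 0 qualifies automatically. Above 0 qualifies if the investigator believes that the person has ADHD, and a DSM diagnosis is already needed. Exactly 0 is left unassigned, which is a drafting gap.

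This matters because efficacy is judged on the same test. The rule treats 0 as a dividing line, since only scores above it need a clinical judgement. It is therefore plausible that participants above 0 show less deficit on TOVA and have less room to improve. If so, the average TOVA effect would be smaller than the effect in participants below 0. A null TOVA result could then mean either no drug effect or limited room to improve, and the plan contains no analysis that would help to tell these apart.

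**Working it through.** **Inputs from the documents.** 53 per arm, 212 evaluable, alpha 0.05, 80% power, 15% drop-out, 244 recruited (Sample size calculation).

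**Assumptions.** The test is two-sided and compares one active arm with placebo using a two-sample t-test. The documents do not give the share above 0 (*f*) or its effect relative to the below-0 group (*r*), so both are varied. The extra variance from mixing two groups is ignored.

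**1. The plan's own figures.** The 53 cannot be reproduced forwards, because no effect size or SD is stated. Solving backwards:

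- Normal approximation: d = (1.960 + 0.842) × √(2/53) = 0.544.
- t-test: d = 0.549, used below.

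The 244 matches 212 × 1.15 = 243.8.

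**2. Overall TOVA comparison.** Average effect = 0.549 × [(1 − f) + f × r], with 53 per arm.

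| Share above 0 | No effect above 0 (r = 0) | Half effect (r = 0.5) | Equal effect (r = 1) |
|---|---|---|---|
| 10% | d = 0.494, power 71% | d = 0.522, power 76% | d = 0.549, power 80% |
| 20% | d = 0.439, power 61% | d = 0.494, power 71% | d = 0.549, power 80% |
| 30% | d = 0.385, power 50% | d = 0.467, power 66% | d = 0.549, power 80% |

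**3. Below-0 participants alone.** Here n per arm = 53 × (1 − f) and d = 0.549.

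| Share above 0 | n per arm below 0 | Power |
|---|---|---|
| 10% | 47.7 | 76% |
| 20% | 42.4 | 71% |
| 30% | 37.1 | 65% |

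With no effect above 0, this beats the overall comparison (71%, 61%, 50%) despite the smaller n. At half the effect the two are about level (76%, 71%, 65% against 76%, 71%, 66%). At equal effect the below-0 analysis loses power against 80%. It therefore belongs in a supportive role.

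**4. Arm-by-stratum interaction, with no effect above 0.** The standard error is √(2/n below + 2/n above) in SD units, and power comes from the normal approximation.

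| Share above 0 | n per arm below / above | SE | 0.549 / SE | Power |
|---|---|---|---|---|
| 10% | 47.7 / 5.3 | 0.648 | 0.85 | 14% |
| 20% | 42.4 / 10.6 | 0.486 | 1.13 | 20% |
| 30% | 37.1 / 15.9 | 0.424 | 1.30 | 25% |

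Even in the scenario that most favours it, the interaction test would usually miss the difference.

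**5. Chance imbalance.** The SD of the difference between two arms in the share above 0 is √[2f(1 − f)/53]. At f = 20% this is √(2 × 0.2 × 0.8 / 53) = 0.078, or about 8 percentage points.

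**The case against.** The strongest reply is that the documents do not supply the premise. They define neither the score nor an upper limit, and the rule itself provides for people above 0 who have ADHD. A reader might infer that those above 0 are in a non-impaired range and face a ceiling, so that the TOVA effect is in fact diluted. The documents do not support that stronger reading. Reduced room to improve is a plausible risk suggested by the shape of the rule.

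A reader might also infer that the rule screens out nobody except a score of exactly 0. That goes too far. The diagnosis criterion does not say who made the diagnosis or when, so an investigator could disagree with a diagnosis on record and exclude someone scoring above 0. The filter is weak but not empty.

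Three further replies have force:

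- The 53 per arm may have been set for the whole eligible population. The mix would then already be allowed for, and no power would be lost against the plan. Nothing in the Sample size calculation settles this.
- The same rule applies in every arm before randomisation, so it creates no bias. Chance imbalance in the share above 0 is ordinary sampling variation, which the standard error covers. Stratification would improve precision; it is not needed for validity.
- The larger gap is that no between-arm method is specified at all, so baseline TOVA can be adjusted for only once a model has been written.

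None of these replies fills the gap at 0 or supplies any plan for baseline TOVA.

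**Conclusion.** The point holds as a modest improvement to the design. The text establishes that the rule sets little effective TOVA threshold, leaves 0 unassigned, and is paired with no stratification, covariate or subgroup by baseline TOVA, although TOVA is a primary measure. The consequence is a possible loss of sensitivity and a null result that is hard to read, confined on this evidence to TOVA.

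The size is unknown. For shares of 10% to 30% above 0, power on one pairwise TOVA comparison runs from 71% down to 50% in the worst case and from 76% down to 66% at half the effect. It does not fall at all if the effect is equal. These figures rest on a back-solved effect of 0.55 SD assigned to the below-0 group and on a two-sided t-test at 53 per arm.

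**What to change.** Leave eligibility otherwise unchanged, and before unblinding:

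1. Define the TOVA score and what 0 represents, and reword the criterion so that a score of 0 falls in one branch.
2. Stratify randomisation by the Visit 1 TOVA score, below 0 versus 0 or above. The test already precedes randomisation at that visit.
3. Specify the between-arm TOVA comparison, adjusted for baseline TOVA and stratum.
4. Pre-specify the TOVA effect in the below-0 stratum as a supportive analysis.
5. Report the arm-by-stratum interaction as descriptive only, given its power of about 14% to 25% per comparison.

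The cost is a two-stratum randomisation list, one reworded sentence and one further planned analysis. No extra visit or assessment is needed. The stratum estimates will be less precise than the overall one, and the supportive analysis adds comparisons across three active arms, so it should not be read as confirmatory.

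### Two unranked primary measures and three oils against one placebo share a single p=0.05, with no success rule or multiplicity control, and the only named test makes no comparison with placebo

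*Combined protocol and SAP*

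**What the plan says.** All references are to the combined protocol and SAP.

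- **Objectives, Primary:** the stated aim is "To assess the efficacy of the cannabis oil treatment containing different concentrations of CBD, THC, CBDV, CBG as per TOVA and Conners test results". The two measures are joined by a plain conjunction. Neither is ranked, and they are not declared co-primary.
- **Background:** the design is given as "In this trial, 3 different types of cannabis oil will be compared to a placebo drug". Placebo is thus the named comparator, giving three oil-placebo contrasts per measure and six over two measures. Allocation is described only as "Participants will be randomized to any of the 4 arms".
- **Sample size calculation:** the section states "In order to detect differences at p=0.05 with 80 % power, 53 participants in each arm (total of 212 participants) will be needed". No endpoint, effect size, SD, test or sidedness is given.
- **Statistical analysis plan:** there are two sentences. The first is "Paired T-tests to assess longitudinal changes in scores before and under treatment will be performed for each participant". The second, on the between-arm analysis, is "In addition, results from the 4 arms will be compared".
- **Visit schedule:** TOVA is listed at Visit 1 and Visit 2 only. Conners is not named at any visit. The nearest entry is "Questionnaires filling (eat, sleep, behavior", listed at all three visits.

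**The concern.** A reader cannot tell from these sections what result would count as success. One oil better than placebo on one measure might be enough, or the same oil might have to win on both. These rules have very different error rates, and nothing in the text prevents the choice from being made after the data are seen.

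The one specified test is also not the comparison for which the trial is randomized. A paired before-after test inside an oil arm picks up practice effects, expectation and regression to the mean along with any drug effect. The between-arm comparison, which removes these, gets one sentence with no method.

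At stake is whether the main conclusion can be read at any stated error level, and whether the 80% power refers to an oil-versus-placebo comparison at all.

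**Working it through.** **1. The plan's own figure.** The arithmetic 4 × 53 = 212 is right. The 53 itself cannot be reproduced, because no effect size or SD is given. Solving backwards at two-sided 0.05 and 80% power:

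- Two-sample contrast, normal approximation: d = √(2/53) × (1.960 + 0.842) = 0.544; by t-test, 0.549.
- Paired t-test: dz = 2.802/√53 = 0.385; by t-test, 0.392.
- Two-sample contrast with Bonferroni over three: d = 0.637.
- Four-arm ANOVA: f = 0.229.

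All four fit 53 per arm, and none of these effect sizes is in the documents. The figure therefore does not show whether three oils or two measures were allowed for.

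**2. Error rate under the rules the text permits.** Inputs from the documents: four arms, equal size implied by 53 per arm, one shared placebo, two measures, 0.05. Assumptions: two-sided tests, only the benefit direction counted (0.025 per test, z > 1.96), and TOVA-Conners correlation ρ from 0 to 0.9. The shared placebo makes oil-placebo contrasts on one measure correlate at 0.5. Simulation with no oil effective:

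| Rule | ρ=0 | ρ=0.5 | ρ=0.9 |
|---|---|---|---|
| Any oil, either measure | 12.1% | 11.0% | 8.7% |
| One measure, any of three oils | 6.3% | 6.3% | 6.3% |
| Omnibus test first on each measure | 4.0% | 3.7% | 2.9% |
| Same oil on both measures | 0.2% | 1.3% | 3.9% |

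Against 2.5% for one test, the first row is 12.1/2.5 = 4.9 times to 8.7/2.5 = 3.5 times as large. The last row lies below 2.5% at ρ = 0.5 and above it at ρ = 0.9.

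**3. The paired test.** Read as a test within each arm of 53, it has noncentrality dz × √53. Suppose, purely as an illustration, that every arm improves non-specifically by dz = 0.2 to 0.3 and no oil works.

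- dz = 0.2: noncentrality 0.2 × 7.280 = 1.456. One arm is significant in 29.8% of trials, and at least one of three oil arms in 1 − (1 − 0.298)³ = 65%.
- dz = 0.3: noncentrality 2.184. One arm is significant in 57.3%, and at least one of three in 1 − (1 − 0.573)³ = 92%.

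These are for one measure only. With no non-specific change the figure is 1 − 0.975³ = 7.3%.

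**4. Candidate gates.** These are familywise errors counting both directions, so the reference is 5% and they are not comparable with the table. Each is the worst case over 0 to 3 oils certain to succeed on the first measure, with every other null true.

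- Bonferroni, with the second measure tested only for an oil that succeeded on the first: each oil contributes at most one first error, so the bound is 3 × 0.05/3 = 5%. Simulated: 4.8% or less.
- Dunnett (z = 2.347) with the same gate: 5.4%, 5.3% and 5.1% at ρ = 0, 0.5 and 0.9.
- One fixed-order chain of six tests at 0.05: 5.0%.

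**The case against.** The strongest reply is that much of this can be read from the text. Placebo is the named comparator, so the three contrasts are identifiable. TOVA is scheduled only at Visits 1 and 2. The analysis compares baseline with the treatment period, and Visit 3 on day 42 falls after the last treatment day (day 32), so the TOVA comparison is evidently Visit 1 against Visit 2. This stands: what is missing is a designation of those contrasts as the primary test, and the timing of Conners.

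A second reply is that the objective's conjunction may mean both measures must succeed, in which case there is little or no inflation. That reading is possible, but the document does not state it. If it were intended, the power for the joint requirement would need stating.

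A third is that the trial is framed as an investigation in a field with limited data, so strict familywise control over three formulations is debatable. The document never calls itself exploratory, however, and it sets a primary efficacy objective, a placebo arm, a significance level and a power. A defined measure and success rule are needed on either view.

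A reader might infer that the plan inflates error whatever rule is used, or that the true rate lies between 0.2% and 12%. The documents support neither. The strictest rule can fall below 2.5%. Both of those ends belong to zero correlation, and 12% is not a ceiling: sidedness is unstated, and one-sided 0.05 tests would give about 22% for any oil on either measure at ρ = 0.

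**Conclusion.** The concern holds: the false-claim rate is undefined, not inflated under every rule. The plan ranks neither measure, states no success rule, controls no multiplicity and designates no between-arm contrast as primary. Which row of the table applies is left open, and the figures rest on two-sided 0.05 tests, the benefit direction, equal arms and an assumed correlation range. The before-after test is a separate weakness. Its 65% to 92% depends wholly on the assumed non-specific improvement and shows how sensitive the test is; it does not predict this trial.

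A reader might also infer that 53 per arm is too few. The documents do not support that, because without an effect size the figure can be neither confirmed nor refuted. The point should be settled before unblinding, since the main conclusion depends on it.

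**What to change.** Before unblinding:

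1. Name one primary measure, as change from Visit 1 to Visit 2, and state at which visits Conners is collected.
2. Make the three oil-versus-placebo between-arm comparisons the primary tests at an overall two-sided 0.05, and write down one of two rules.
   - **Bonferroni:** 0.05/3 per oil on the primary measure. The second measure is tested for an oil only if that oil succeeded on the first, at the same level.
   - **Fixed order:** one pre-declared chain at 0.05, the three oils on the first measure and then the second measure, stopping at the first failure.
3. Use Dunnett only if the primary measure alone is confirmatory, since with oil-by-oil gating it slightly exceeds 5%.
4. Label the paired t-tests and oil-versus-oil comparisons exploratory.
5. Restate the sample-size line with endpoint, effect size, test, sidedness and the power of the adjusted test.

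The cost is protocol and SAP wording; no extra participants are proposed. The downside of Bonferroni is lower stated power. As an illustration only, at d = 0.55 and 53 per arm, 80% unadjusted becomes about 66%, and regaining 80% would take about 71 per arm. Under the fixed order, later oils may never be formally tested, and the second measure is reached only if all three oils succeed on the first.

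### The 15% drop-out allowance is added to 212 rather than divided out: 244 recruits leave about 207 evaluable, not 212, if drop-outs have no day-26 score (minor, about 1 point of power)

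*Combined protocol and SAP*

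**What the plan says.** The Sample size calculation section states its target, "In order to detect differences at p=0.05 with 80 % power", and the number this requires: "53 participants in each arm (total of 212 participants) will be needed". It then allows for losses: "With an estimation of 15% drop-out, 244 participants will be recruited". It names no inflation formula, effect size, standard deviation, test or sidedness. It does not define drop-out or say when the 15% is expected to occur.

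Three other places decide which participants count as evaluable:

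- **Statistical analysis plan:** "Paired T-tests to assess longitudinal changes in scores before and under treatment will be performed for each participant". The four arms are also to be compared, by a method that is not named.
- **Methods, visit schedule:** TOVA is listed at Visit 1 and at "Visit 2: end of treatment, day 26". The day-14 follow-up lists adverse events, medication changes and a blinding questionnaire, with no efficacy test. Visit 3, on day 42, has questionnaires but no TOVA.
- **Dose regimen:** "Day 32 will be the last day of treatment". Visit 3 therefore falls after treatment has ended.

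The document has no rule on replacement, imputation or analysis sets.

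**The concern.** A drop-out rate is normally a proportion of the people recruited. To keep a required number after losing a fraction d, the requirement is divided by (1 − d). Multiplying by (1 + d) gives too few, because the loss applies to the larger recruited number and not to the 212. The figure of 244 is what multiplication gives.

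The shortfall matters only if people who drop out supply no score for the analysis. The planned paired comparison needs one score before treatment and one during it, and Visit 2 is the only source of the second. Anyone lost before Visit 2 has no pair, and nothing in the plan lets that person count toward 212. What is at stake is whether the recruitment target delivers the number that the same paragraph says is necessary.

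**Working it through.** **Inputs.** Sample size calculation section: 53 per arm and 212 in total, 15% drop-out, 244 recruited, p = 0.05, 80% power. Background: four arms; equal allocation is implied by 53 in each.

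**1. Reproduce the plan's figure.**
- In total: 212 × 1.15 = 243.8, rounded up to 244.
- Per arm: 53 × 1.15 = 60.95, rounded up to 61, and 61 × 4 = 244.

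Both routes give exactly 244. Multiplication is inferred from this match, since the plan does not name its formula.

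**2. Treat 15% as a share of recruits.**
- In total: 212 / 0.85 = 249.4, so 250.
- Per arm: 53 / 0.85 = 62.35, so 63, and 63 × 4 = 252.

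**3. What 244 delivers if the 15% leave before Visit 2.**
- Evaluable: 244 × 0.85 = 207.4, or 207.4 / 4 = 51.85 per arm.
- Shortfall: 212 − 207.4 = 4.6, about 5 participants.

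**4. The drop-out that 244 can absorb.**
- (244 − 212) / 244 = 32/244 = 13.1%.
- At 15%, expected drop-outs are 244 × 0.15 = 36.6. For 212 to hold, 36.6 − 32 = 4.6 of them must still have a day-26 score: 4.6 / 36.6 = 12.6%, about 1 in 8.

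**5. Power.** With no effect size in the plan, the loss is measured relative to the plan's own claim. For each candidate test, take the difference that 53 per arm detects with exactly 80% power, then recompute power at 51.85 per arm (noncentral t or F):

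| Test | Power at 51.85 per arm |
|---|---|
| Two-sample t, two-sided 0.05 | 79.1% |
| Two-sample t, one-sided 0.05 | 79.2% |
| Two-sample t, Bonferroni for 3 comparisons | 79.0% |
| Two-sample t, Bonferroni for 6 comparisons | 78.9% |
| Paired t within arm, two-sided 0.05 | 79.1% |
| Paired t within arm, one-sided 0.05 | 79.2% |
| Four-group F-test, 0.05 | 79.0% |

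The loss is about 1 point whichever test was meant.

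**6. Chance of reaching 212.** Assume independent drop-out at 15%, all before Visit 2. The binomial probability of at least 212 evaluable is 23% with 244 recruits, 58% with 250 and 69% with 252.

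**The case against.** The strongest reply is that the shortfall is conditional. The plan does not say that 15% is a share of recruits; read as recruiting 15% more than needed, 244 is correctly rounded. Drop-out is also undefined. Only about 5 of some 37 expected drop-outs need a day-26 score for 212 to hold, and there are two plausible routes. Some may leave between day 26 and the day-42 visit. Others may stop the oil early, which the Treatment cessation section provides for, and still attend Visit 2. The Methods section also mentions two phone contacts but describes only one, so the content of the second is unknown, although a TOVA test by phone is unlikely.

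All of this is possible, but the plan relies on none of it. Both routes fall within the condition stated here, that drop-outs have no day-26 score. If the sponsor had one of them in mind, saying so is itself the correction.

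The second reply is size. The recruitment gap is about 2.5% (244 against 250), and the detectable standardised difference in a two-sided two-sample test rises by only about 1.1% (0.549 to 0.555). Uncertainty in the 15% estimate is larger than that. This stands: the point is minor. The binomial figures should not make it look bigger, since even the standard answer of 250 reaches 212 only 58% of the time.

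The third reply is that quoting 79% could make an unsupported 80% look verified. That is a fair caution. The 79% is meaningful only relative to 53 per arm giving 80%, which cannot be checked without an effect size, and it should be worded that way.

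**Conclusion.** The concern holds, and it is minor. At the plan's own 15% drop-out, 244 recruits leave about 207 evaluable participants (about 52 per arm) against the 212 stated as needed. Power is 78.9% to 79.2% in place of 80%. The figure of 244 is enough only if drop-out before day 26 stays at or below about 13%.

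This rests on three assumptions: 15% is a proportion of those recruited, the drop-outs leave before Visit 2, and they contribute no on-treatment score. The plan states nothing to the contrary. The power figures also take as given that 53 per arm yields exactly 80%, which the document does not allow anyone to confirm.

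**What to change.** Change one sentence in the Sample size calculation section, in either of two ways:

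- State that 244 will be recruited (61 per arm); that with 15% drop-out before the day-26 visit about 207 will be evaluable (about 52 per arm); and that power is then about 79% for the difference that 53 per arm would detect with 80% power.
- Or keep 244 and 212, and state that 212 evaluable holds only for drop-out before day 26 of up to about 13%.

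Either version should say what counts as drop-out and at which visit.

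Neither needs more participants. The only cost is a stated power of about 79% or a stated drop-out limit of about 13%. For reference, 15% drop-out with 212 evaluable corresponds to 250 recruits, or 252 (63 per arm) for four equal arms. The effect size and test behind 53 per arm are for the sponsor to supply and should not be back-solved into the plan.
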